10.1 AE of Special Interest

In this study an AE of special interest is:

• RBP-6000 depot removal (see Section 10.7)

This AE of special interest should be reported to Indivior, by the Investigator (or designee) **within 24 hours** from first being aware of the event, using the same reporting process as for SAEs, See Section 11.2.

For the first induction day/Day 1, Investigators also will be asked to identify any AEs that were associated with precipitated withdrawal, if based on their clinical judgment, precipitated withdrawal occurs.

10.2 Assessing and Documenting Adverse Events

The Investigator is ultimately responsible for assessing and reporting all AEs as outlined in the protocol. The assessment and reporting of AEs may be delegated to a medically qualified sub-Investigator, trained on this study protocol, who is listed on the delegation of authority log. All AEs regardless of treatment group or suspected causal relationship to the study drug will be reported as described in this protocol.

Adverse events should be volunteered by the participant or solicited from the participant using a standard statement, obtained from examination of the participant at a site visit, or from observations of clinically significant laboratory values or special examination abnormal values. If an event assessed by one of the study scales requires intervention, or if in the opinion of the Investigator, it is clinically significant, then it will be reported as an AE.

All AEs are to be assessed and recorded in a timely manner and followed to resolution or until the Investigator determines that there is not an anticipated resolution. Each AE is to be documented with reference to intensity (severity), date of occurrence, duration, treatment and outcome. Furthermore, each AE is to be classified as being serious or non-serious. In addition, the Investigator must assess whether the AE is study drug-related or not, whether the AE is an opioid withdrawal symptom and whether a concomitant medication was given. This should be documented in the eCRF.

10.3 Time Period for Collecting Adverse Events

Adverse events will be collected from the time of signed informed consent until completion of the EOT/ET visit. Thereafter, participants will be contacted by telephone to assess AEs that were ongoing at the EOT/ET visit and concomitant medications associated with those ongoing AEs. Participants do not need to return to the site unless deemed medically necessary by the Investigator.

Participants with ongoing SAEs at the EOS telephone contact that, in the opinion of the Investigator, are associated with the study drug, will be followed and reported as described in Section 11. Participants with ongoing AEs at EOS telephone contact will not be followed up further.

10.4 Assessment of Intensity

The term "severe" is used to describe the intensity (severity) of a specific event (as in mild, moderate, or severe); the event itself, however, may be of relatively minor medical significance (such as a severe headache). This is not the same as "serious," which is based on participant/event outcome or action criteria usually associated with events that pose a threat to a participant's life or functioning. Seriousness (not severity) serves as a guide for defining regulatory reporting obligations.

Intensity	Definition
Mild	Causes transient or mild discomfort; no limitation of usual activities; no medical intervention required
Moderate	Causes mild to moderate limitation in activity; some limitation of usual activities; no or minimal medical intervention or therapy is required
Severe	Causes marked limitation in activity; some assistance is usually required; medical intervention or therapy is required; hospitalisation is probable

Adverse events with changes in severity should be documented as separate events.

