Approval from the sponsor must be obtained for any local laboratory and the laboratory normal ranges utilized to determine eligibility for screening. If a local laboratory is utilized for eligibility, the laboratory samples will also be sent to the central laboratory for the baseline analysis value.

If eligibility is confirmed at the screening visit, participants may complete the induction visit. Participants having same-day screening and induction visits are not required to repeat the UDS, pregnancy test, vitals and ECG for the induction visit.

On induction days, eligible participants will provide a urine sample for a UDS dipstick and pregnancy test (female participants of child-bearing potential only). If a female participant has a positive pregnancy test, she will be discontinued and will not proceed with subsequent assessments. The Investigator will ask him/her to self-report recent drug use (including the use of a TLFB assessment). The Investigator may discuss any positive UDS results with the participant only after completion of the TLFB:

- Participants who report that they have used long-acting opioids within the
 previous 24 hours will not be permitted to proceed with induction until the
 24-hour period has passed. If necessary, induction may be rescheduled. The 1st
 day of the repeat induction should be scheduled within 30 days of informed
 consent.
- 2. Participants who have used short-acting opioids within the previous 6 hours may be permitted to proceed with the induction visit at the discretion of the Investigator.

All concomitant medications used since Screening will be reviewed.

The COWS will then be completed to assess withdrawal symptoms.

Participants must meet **both** of the following criteria to receive TM buprenorphine:

- 1. Have a negative pregnancy test (if female and of childbearing potential)
- 2. Be in withdrawal (COWS score ≥ 8)

If a participant's COWS score is <8, the participant may either be re-scheduled for induction within 30 days of informed consent or remain at the site (at the Investigator's discretion), and the COWS may be repeated until the participant has a score \geq 8. Only when the COWS score is \geq 8 and all pre-TM buprenorphine assessments have been completed may the participant receive TM buprenorphine to begin induction.

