#### **5.4.2.1** Definition of endpoints

These endpoints will encompass all induction attempts, and therefore utilise the first dose of TM BUP for derivations. A treatment-emergent adverse event (TEAE) is defined as an AE having an onset date/time after administration of the first TM BUP dose and before the date/time of Injection 3. The TEAEs are classified into the 2 consecutive time intervals, defined as:

• TEAEs up to RBP-6000 Injection 2 are TEAEs with a start date/time on or after the first dose of TM BUP and before the date/time of Injection 2

 TEAEs between RBP-6000 Injections 2 and 3 are TEAEs with a start date/time on or after Injection 2 and before the date/time of Injection 3

Note: If AE onset time is missing, then only the onset date will be used to assign TEAE status. An AE onset date on or after the date of the administration of the first dose of TM BUP will be considered a TEAE.

For participants who received Injections 1 and 3 (but not Injection 2), their TEAE with start date before the date of Injection 3 will be classified into the time interval of "up to RBP-6000 Injection 2". For discontinued participants whose last injection was Injection 1, their TEAE with start date after the last injection will be classified into the time interval of "up to RBP-6000 Injection 2". For discontinued participants whose last injection was Injection 2, their TEAE with start date after the last injection will be classified into the time interval of "between RBP-6000 Injections 2 and 3".

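### Severity changes open new adverse event records and the SAP classifies by start date/time alone, so an event that only improves can enter Endpoint 2 or enter Endpoint 3 a second time

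*Protocol*

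**What the plan says.** Four provisions bear on this.

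- Protocol 10.3: "Adverse events will be collected from the time of signed informed consent until completion of the EOT/ET visit". Events arising before any study drug are therefore in the database.
- Protocol 10.2: "Each AE is to be documented with reference to intensity (severity), date of occurrence, duration, treatment and outcome". Every record carries its own intensity and its own date.
- Protocol 10.4: "Adverse events with changes in severity should be documented as separate events". No direction of change is given.
- SAP 5.4.2.1: a TEAE "is defined as an AE having an onset date/time after administration of the first TM BUP dose and before the date/time of Injection 3". For the second interval, "TEAEs between RBP-6000 Injections 2 and 3 are TEAEs with a start date/time on or after Injection 2" and before Injection 3. Where the clock time is absent, "If AE onset time is missing, then only the onset date will be used to assign TEAE status".

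Neither document makes worsening a condition of TEAE status, links the records of one event, or collapses them before classification. SAP 5.6.2 counts a participant once per preferred term, at the worst severity, but only among records already classed as TEAEs. SAP 5.4.2.2 and 5.4.2.3 summarise the two intervals separately.

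**The concern.** Each rule is workable alone; the difficulty lies in the combination. Splitting an event at each severity change is a legitimate way to collect data. Classifying on start date/time is safe when one record is one event. Together, they let the second half of an improving event look like a new event if the improvement falls after the first TM buprenorphine dose or after Injection 2.

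This sits badly with Protocol 10, which describes an adverse event as something new or exacerbated. An event that has eased is neither. Endpoints 2 and 3 are the sub-study's safety endpoints, and some of what they report as events could be recovery.

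**Working it through.** The documents give no figure to reproduce, so the check applies the stated rule to example records and then gives an assumed range.

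**Step 1: the rule.** Take the first TM buprenorphine dose as day 1, Injection 2 as day 8 and Injection 3 as day 36. The records are invented, and each follow-on record is assumed to start on the day severity changed.

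| Record | Start day | SAP 5.4.2.1 as written | With a worsening condition |
|---|---|---|---|
| Nausea, moderate | -3 | Not a TEAE | Not a TEAE |
| Same nausea, eased to mild | 2 | TEAE up to Injection 2 | Not a TEAE |
| Headache, moderate | 4 | TEAE up to Injection 2 | TEAE up to Injection 2 |
| Same headache, eased to mild | 12 | TEAE between Injections 2 and 3 | Kept under the day 4 onset |

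The written rule yields three TEAE records. One is a genuine onset.

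**Step 2: do other rules catch it?** Counting once per preferred term does not help the nausea: its pre-dose record is not a TEAE, so the milder record is the only one counted. It does not help the headache in Endpoint 3 either, because nothing applies that count across the two intervals. In the tables of SAP 5.6.2 covering the whole sub-study, the headache participant is counted once for that term at moderate severity, so the error there is nil. For this second case the fault is a false second entry, not a false first one.

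**Step 3: how a participant-level proportion moves.** Let p be the true proportion with a TEAE in the interval, and q the proportion carrying in an event that only improves during it. Assuming independence:

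- observed proportion = p + (1 − p)q, so the increase is (1 − p)q.

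The documents give neither p nor q. For assumed p of 20% to 60% and q of 2% to 10%:

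- smallest increase: (1 − 0.60) × 0.02 = 0.008, or 0.8 percentage points;
- largest increase: (1 − 0.20) × 0.10 = 0.080, or 8.0 percentage points.

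Of the planned 489, that is 489 × 0.008 = 3.9 to 489 × 0.080 = 39.1 participants for Endpoint 2. For Endpoint 3 the denominator is SFAS participants who received Injection 2. At the planning retention of 70% (SAP 3) that is about 0.70 × 489 = 342, giving 342 × 0.008 = 2.7 to 342 × 0.080 = 27.4. The 489 is the planned number, not the final SFAS.

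The factor (1 − p) shows the limit: a participant with another qualifying TEAE in the interval is already counted. Masking is weaker in narrow categories, such as a single preferred term, where p is smaller.

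**The case against.** The strongest objection is that few events are open to this error. A reader might infer that it is widespread, because Protocol 4.1.1 requires participants to "Be in withdrawal (COWS score" of at least 8) before TM buprenorphine. The documents do not support that. Protocol 10 excludes the expected signs and symptoms of the disorder under study unless they exceed what is expected, and the usual fluctuation of conditions present at study start that do not worsen. Protocol 10.2 makes a scale-assessed finding an adverse event only if it needs intervention or is judged clinically significant. Ordinary pre-dose withdrawal will mostly leave no record that could later improve. This stands, and it shrinks the Endpoint 2 case to events arising between consent and first dose that fall outside those exclusions. It does not reach the Endpoint 3 case, which concerns events already accepted as TEAEs.

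Second, the start date of the follow-on record is inferred. It is the natural reading of Protocol 10.2 with 10.4, but Protocol 16 promises CRF completion guidelines that are not supplied and could settle it differently. This stands as a condition on the conclusion.

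Third, both endpoints are descriptive in SAP Table 2, with no test or decision attached, and any overcount errs towards reporting more harm. That limits the consequence but does not make the proportions correct.

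**Conclusion.** The point holds in a limited form. If a separate severity record starts on the date of the change, SAP 5.4.2.1 as written counts a pre-dose event that only eases as a TEAE up to Injection 2, and counts a first-interval TEAE that only eases after Injection 2 again in the next interval. Both effects are confined to participants with no other qualifying TEAE in that interval or category. The 0.8 to 8.0 point range is illustrative; the true size cannot be determined from the documents and could be close to zero. The primary retention endpoint is untouched.

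Two further inferences should be resisted. One is that the comparison of rapid with SoC induction is biased in a known direction. Injection 2 falls at different distances from the first TM buprenorphine dose in the two arms, so unequal carry-over is conceivable, but no figure shows its size or which arm would be favoured. The other is that the 300 mg versus 100 mg comparison in the double-blind period is affected. This SAP covers the sub-study only, and the main-study TEAE rule is not in the supplied text.

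**What to change.** Change SAP 5.4.2.1 only.

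- Link consecutive severity records of one event: same participant, same preferred term, contiguous dates.
- Give a follow-on record TEAE status, or entry into a later interval, only if its severity is worse than the pre-dose or prior-interval severity.
- Otherwise keep it under the original onset.

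The text should also say which severity is the reference when several were recorded before the boundary, the last or the worst.

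Protocol 10.4 need not change. Sites can go on recording each severity level, and altering that during the study would leave records made under two conventions.

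The cost is some extra derivation code; no new data are needed. The downside is that linking by preferred term and contiguous dates may occasionally merge two distinct events, so all linked records should be listed for review.

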10.5 Assessment of Causality

The Investigator or a medically qualified sub-Investigator, trained on this study protocol, listed on the delegation of authority log is responsible for determining the AE relationship to the study drug.

The following categories will be used to define the relationship of an AE to the administration of the study drug:

Not Related: Data are available to identify a clear alternative cause for the AE other

than the study drug.

Related: The cause of the AE is related to the study drug and cannot be reasonably

explained by other factors (e.g., the participant's clinical state,

concomitant therapy, and/or other interventions).

A "reasonable possibility" is meant to convey that there are facts/evidence or arguments to suggest a causal relationship, rather than that a relationship cannot be ruled out. The Investigator will use clinical judgment to determine the relationship. Alternative causes, such as natural history of the underlying diseases, concomitant therapy, other risk factors and the temporal relationship of the event to the study drug will be considered and investigated. The Investigator will also consult the applicable product labelling information in the determination of his/her assessment. For each AE/SAE, the Investigator must document in the medical notes that he/she has reviewed the AE/SAE and has provided an assessment of causality.

There may be situations when an SAE or AE of special interest has occurred and the Investigator has minimal information to include in the initial report to Indivior or designated representative. However, it is imperative that the Investigator always make an assessment of causality for every event prior to the initial transmission of the SAE or AE of special interest data to Indivior or designated representative. The Investigator may change his/her opinion of causality in light of follow-up information and amend the SAE or AE of special interest data collection tool accordingly. The causality assessment is one of the criteria used when determining regulatory reporting requirements.

10.6 Clinical Laboratory, Vital Signs, and Other Safety Findings

Changes in laboratory values, vital signs or other safety parameters (e.g., neurological and clinical symptom assessments) as noted in the protocol are a sub-set of AEs and are reportable only if the lab test result is associated with accompanying symptoms, and/or requires additional diagnostic testing or intervention (medical, surgical), and/or requires additional significant treatment, and/or requires temporal or permanent discontinuation of study drug, or a change to dosing other than as permitted by protocol, or if considered to be clinically significant by Investigator or medically qualified designee.

Guidance for the procedures to follow for elevated liver function tests are provided in Appendix 22.7.

All ECG findings that are considered abnormal and clinically significant should be evaluated for a change from baseline and must be captured as AEs.

10.7 RBP-6000 Depot Removal

If clinically indicated, the RBP-6000 depot may be surgically removed within 14 days of injection. Any occurrence of depot removal will be captured in the database as an AE of special interest. In addition, the AE that resulted in the depot removal needs to be reported; this is not an AE of special interest. Additional details about the depot removal (e.g., the reason for the removal, whether the depot was removed by the participant or the Investigator, and whether this was voluntary or involuntary [i.e., whether the participant agreed to the removal]) also need to be reported. Depot removal should be reported using the same timing as for SAEs (see Section 11.2.1).

11 SERIOUS ADVERSE EVENT

11.1 Definition of Serious Adverse Event

The Investigator or designee is responsible for identifying, documenting and reporting events that meet the definition of an SAE.

An SAE is any event that meets any of the following criteria:

- Death
- Life-threatening
- Inpatient hospitalisation or prolongation of existing hospitalisation
- Persistent or significant disability/incapacity
- Congenital anomaly/birth defect in the offspring of a participant who received RBP-6000
- Other: Important medical events that may not result in death, be life-threatening, or require hospitalisation, may be considered an SAE when, based upon appropriate medical judgment, they may jeopardise the participant and may require medical or surgical intervention to prevent one of the outcomes listed in this definition. Examples of such events are:
 - o intensive treatment in an emergency room or at home for allergic bronchospasm
 - o blood dyscrasias or convulsions that do not result in inpatient hospitalisation
 - o development of drug dependency or drug abuse
- Laboratory values of ALT or AST >3×ULN and bilirubin >2×ULN are defined as SAEs (important medical event), and should be reported to Indivior (or designated representative), by the Investigator (or designee) within 24 hours from first being aware of the event, using the same reporting process as for SAEs, See Section 11.2.1. Potential Hy's Law cases should be managed as described in 22.7.

An AE is considered "life threatening" if the participant was at immediate risk of death from the event as it occurred; i.e., it does not include a reaction that if it had occurred in a more serious form might have caused death. For example, study drug-induced hepatitis that resolved without evidence of hepatic failure would not be considered life threatening even though study drug-induced hepatitis can be fatal.

Any AEs requiring hospitalisation should be considered SAEs. Hospitalisation for elective surgery or routine clinical procedures that are not the result of AE (e.g., elective surgery for a pre-existing condition that has not worsened) should not be considered AEs or SAEs. If anything untoward is reported during the procedure, that occurrence must be reported as an AE (either "serious" or "non-serious") according to the usual criteria.

In general, hospitalisation signifies that the participant has been detained (usually involving at least an overnight stay) at the hospital or emergency ward for observation and/or treatment that would not have been appropriate in the physician's office or other outpatient setting. Complications that occur during hospitalisation are AEs. If a complication prolongs hospitalisation or fulfils any other serious criteria, the event is serious. When in doubt as to whether "hospitalisation" occurred or was necessary, the AE should be considered serious.

An AE is incapacitating or disabling if the experience results in a substantial and/or permanent disruption of the participant's ability to carry out normal life functions.

11.2 Documenting Serious Adverse Events

When an SAE occurs, it is the responsibility of the Investigator to review all documentation (e.g., hospital progress notes, laboratory and diagnostic reports) pertaining to the event. The Investigator will then record all relevant information regarding an SAE on the appropriate electronic or paper form(s).

It is not acceptable for the Investigator to send photocopies of the participant's medical records to Indivior in lieu of completion of the SAE Reporting Form. However, there may be cases where copies of medical records are requested by Indivior or designated representative. In this instance, all participant identifiers, with the exception of participant number, will be redacted on the copies of the medical records prior to submission to Indivior.

The Investigator will attempt to establish a diagnosis of the event based on signs, symptoms, and/or other clinical information. In such cases, the diagnosis will be documented as an AE or SAE and not the individual signs/symptoms.

11.2.1 Investigator Reporting of Serious Adverse Events

Once the Investigator determines that an event meets the protocol definition of an SAE, the SAE will be reported to Indivior Global Safety (or designated representative) by the Investigator (or designee) within 24 hours from first being aware of the event. Any follow-up information on a previously reported SAE will also be reported to Indivior Global Safety within 24 hours.

Where additional information is needed or expected, the Investigator will not wait to receive all information before reporting the event to Indivior. The Investigator must provide an assessment of causality at the time of the initial report as described in Section 10.5 of the protocol.

In the event of an SAE, the Investigator or designee will notify Indivior Global Safety by completing the appropriate form(s) in the eCRF. Follow-up information will also be reported in the eCRF.

In the event that the electronic data capture system is not available, a paper Safety Information Collection Form should be completed and submitted to Indivior Global Safety via email or fax:

When the electronic data capture system is again available, the information recorded on the paper Safety Information Collection Form should be entered into the eCRF.

